2. STUDY PROCEDURES

a. Procedures

The children will be referred from Stanford Youth Solutions and UCSF CAS. UCSF has approved recruitment at their site and they have provided their own consent forms. Some children may also be self-referred from the community as a response to a flyer that may have been distributed to them in a public forum, from a community organization, from a physician/pediatrician, or a hospital setting.

School staff will speak with parents of children they have identified as potential study candidates and with verbal consent will submit parent's name and phone number so that the research coordinator can make contact directly to conduct phone screening. School staff may also obtain verbal consent for a Stanford research team member to come to the school site and do informed consent process and screening at school for any participants that may have

transportation barriers.

Caregivers will undergo a telephone or in-person screening according to the inclusion and exclusion criteria. Written consent for participation will be obtained from participants, parents and/or legal guardians. Participants will be randomly assigned to one of three treatment conditions: TF-CBT, CCT, or TAU. Assessments will be administered at 4 time points: 1) pre-treatment, 2) mid-therapy, 3)post-treatment, and 4) three month follow-up. A medical/developmental history form will be completed only pre-treatment. The vocabulary and block design subtests of the Wechsler Abbreviated Scale of Intelligence (WASI-II) will be administered only pre-treatment to rule out potential confounds for neuroimaging. The UCLA PTSD Reaction Index (PTSD-RI) parent and child versions will be used to assess exposure to traumatic events and posttraumatic stress symptoms. Given that trauma has high comorbidity with depression and anxiety disorders these symptoms will be assessed using the Multidimensional Anxiety Scale for Children (MASC), Children's Depression Inventory (CDI), and Trauma Symptom Checklist for Children (TSCC) or Trauma Symptom Checklist for Young Children (TSCYC). Executive functioning will be assessed by both child and parent report using the Behavioral Rating Inventory of Executive Function (BRIEF) and the Brief Impairment Scale (BIS) for the parent. A post-treatment services form will be completed only at the three month follow up appointment.

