3. BACKGROUND

a. Past Experimental and/or Clinical Findings

A previous RCT of CCT (Carrion et al., 2013), sought to examine the efficacy of the intervention as a short-term, manual-based intervention for youth in the school setting with interpersonal violence exposure undergoing concurrent and chronic environmental adversity. The study findings, published in the Journal of Traumatic Stress (Carrion et al., 2013), utilized hierachal linear modeling analyses to show that compared to the waitlist group, the cue-centered treatment group had greater reductions in PTSD symptoms both by caregiver and child report, as well as caregiver anxiety. Cue-centered treatment, a hybrid trauma intervention merging diverse theoretical approaches, demonstrated feasibility, adherence, and efficacy in treating youth with a history of interpersonal violence.

The previous RCT proved the efficacy of CCT compared to a waitlist group. The next step therefore, is to compare CCT to an active treatment which we chose to be TF-CBT due to the numerous RCTs proving the efficacy of TF-CBT in reducing trauma and associated symptoms. However, about 20-30% of youth do not respond to cognitive-behavioral therapies.

b. Findings from Past Animal Experiments

N/A

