k. Payments to Participants

Participants who complete all behavioral assessments and fNIRs at each time phase will receive a \$25 gift card (a total of \$100) which will incentivize participants to complete the assessments.

l. Costs to Participants

There are no costs to the participant.

m. Planned Duration of the Study

The entire duration of the study will be 4.5 years ending in July 2020.

- (i) 10-15 minutes for screening of participants
- (ii) 15-18 weekly 45-minute treatment sessions over the duration of 3 months. There will be completion of 3 hour behavioral assessments over 4 time points (pre-, mid-, post-treatment and six month follow-up). Participants will also do 45-60 minutes of fNIRs imaging at each of the time points.
- (iii) Participant data will be processed and analyzed per participant, but mostly in bulk. Participant data will be analyzed periodically throughout the length of the study. After data acquisition, data will be checked for quality and will be double-entered. Analysis will be within and between groups.

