# Child Characteristics, Neuromarkers, and Intervention Components Impacting Treatment Outcome: CCT, TF-CBT, TAU

NCT02926677

9/18/20

[name], Principal Investigator  
Stanford University  
Stanford, California 94305

Planned Sample Size: Analyses will be conducted on data for participants that completed treatment from baseline to month 3 (end of treatment). The sample size is 8 participants for the CCT group, 8 for TF-CBT, and 6 for TAU.

Planned Analyses: Factorial ANOVAs comparing baseline to month 3 (end of treatment) total scores on all outcome measures (UCLA PTSD Reaction Index for DSM 5 child and parent versions, Child Depression Inventory, Multidimensional Anxiety Scale for Children, Behavior Rating Inventory of Executive Function) will be conducted for each treatment arm.

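### The SAP's factorial ANOVA names neither a within-child term nor a baseline covariate for paired scores; a baseline-adjusted comparison of the three arms would be better defined and more powerful.

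*SAP*

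**What the plan says.** The SAP gives one sentence of method under Planned Analyses: "Factorial ANOVAs comparing baseline to month 3 (end of treatment) total scores on all outcome measures". It then lists the measures (child and parent PTSD Reaction Index, depression, anxiety, executive function) and says that the ANOVAs "will be conducted for each treatment arm". Under Planned Sample Size it restricts the analysis to children who completed treatment through month 3: "The sample size is 8 participants for the CCT group, 8 for TF-CBT, and 6 for TAU".

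The SAP states no error term, subject term, covariance structure, paired test or baseline covariate. It gives no alpha, effect size, SD, pre-post correlation or power.

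The protocol adds little. Section 2.a sets repeated assessment of each child: "Assessments will be administered at 4 time points: 1) pre-treatment, 2) mid-therapy, 3)post-treatment, and 4) three month follow-up". Section 5.m says only "Analysis will be within and between groups". Section 3.a reports that the earlier randomised trial of CCT against a waitlist "utilized hierachal linear modeling analyses to show that compared to the waitlist group", CCT gave greater symptom reduction. The first objective in section 1 is between-arm: whether TF-CBT and CCT do better than TAU.

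**The concern.** Baseline and month-3 scores from the same child are normally correlated, and a valid test of change must use that pairing. The SAP's sentence leaves two things open: whether time is a within-child factor, and whether the ANOVA is a separate pre-post test in each arm or a 3 (arm) x 2 (time) layout. Two analysts could both follow it and report materially different p-values from the same data.

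If the pairing is ignored, tests of change and of arm-by-time lose power in arms of 6 to 8, and a test of the arm main effect produces too many false positives. If the pairing is respected, a smaller problem remains. The arm-by-time test is a comparison of change scores, which uses the baseline less efficiently than adjustment for it. In addition, separate ANOVAs by arm would not give the between-arm comparison in the first objective.

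**Working it through.** **Inputs from the documents.** Arms of 8, 8 and 6, so 8 + 8 + 6 = 22 children and 2 x 22 = 44 scores per measure. The plan gives no power or precision figure to reproduce.

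**Assumptions, none stated in the documents.** Two-sided alpha 0.05; normal scores with the same SD at both times; correlation r between a child's two scores from 0 to 0.7; effects in SD units.

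**Step 1: standard errors if pairing is ignored.**
- Change: the true variance per child is 2·SD²·(1-r). The independent analysis uses 2·SD². Its SE is too large by 1/sqrt(1-r): 1/sqrt(0.7) = 1.20, 1/sqrt(0.5) = 1.41, 1/sqrt(0.3) = 1.83 at r = 0.3, 0.5, 0.7. The same factor applies to arm-by-time.
- Arm main effect, averaged over both times: the true variance per child is SD²·(1+r)/2. The independent analysis uses SD²/2. Its SE is too small by 1/sqrt(1+r): 0.88, 0.82, 0.77 at the same correlations. Simulated type I error (20,000 runs, 8/8/6) is about 10%, 13% and 17% instead of 5%.

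**Step 2: one arm of 8, true change 0.8 SD.** The independent two-sample t test (14 df) was simulated with 200,000 runs. Paired power is exact from the noncentral t (7 df).

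| r | Type I error, independent | Power, independent | Power, paired |
|---|---|---|---|
| 0 | 5.0% | 32% | 28% |
| 0.1 | 4.0% | 31% | 31% |
| 0.3 | 2.4% | 30% | 38% |
| 0.5 | 1.0% | 28% | 50% |
| 0.7 | 0.3% | 25% | 71% |

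At r of about 0.1 or below nothing is lost, because the paired test has half the degrees of freedom. In the arm of 6 the figures are 19% against 36% at r=0.5 and 17% against 53% at r=0.7.

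**Step 3: comparison between arms.** A change-score contrast has variance 2·SD²·(1-r) per child. A baseline-adjusted contrast has approximately SD²·(1-r²), ignoring chance baseline imbalance. The ratio is (1-r²)/[2(1-r)] = (1+r)/2: 0.50, 0.55, 0.65, 0.75 and 0.85 at r = 0, 0.1, 0.3, 0.5 and 0.7. It is below 1 for any r below 1. The price is one error degree of freedom: 22 - 3 = 19 becomes 18.

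Simulated power at 8/8/6, with both active arms 1 SD better than TAU at month 3:

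| r | Independent factorial, arm-by-time | Repeated-measures, arm-by-time | ANCOVA |
|---|---|---|---|
| 0 | 23% | 21% | 37% |
| 0.1 | 21% | 23% | 38% |
| 0.3 | 17% | 29% | 40% |
| 0.5 | 12% | 40% | 48% |
| 0.7 | 7% | 60% | 64% |

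Repeat simulations agree within about two percentage points. ANCOVA keeps its type I error near 5% (5.0% at r=0.5, 5.1% at r=0.7).

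**The case against.** A reader might infer that the SAP analyses 44 scores as 44 independent observations, so that its standard errors are too large and much of its power is lost. The documents do not support that as a statement of fact, for these reasons:
- Factorial means only that factors are crossed. An arm-by-time ANOVA with time repeated is a factorial ANOVA, and an analysis set of children followed from baseline to month 3 fits that reading without proving it. If time is within-child, Steps 1 and 2 do not apply.
- Even if pairing is ignored, the error does not run one way. It is conservative for change and arm-by-time and anti-conservative for the arm main effect.
- The size depends on a correlation that the documents do not give. Within an arm the loss is nil near r=0.1 and modest at 0.3.
- The use of hierarchical modelling in the earlier CCT trial shows that repeated scores were handled there. It does not show that they are ignored here.

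All four points stand. It can also be said that the gap between the independent ANOVA and ANCOVA overstates the cost of ignoring pairing, and that declaring time a within-child factor would be enough. The first part is right: at r=0.5, of the 36 points between 12% and 48%, 28 (12% to 40%) come from pairing and 8 (40% to 48%) from baseline adjustment. The second part holds only for the ambiguity. A repeated-measures declaration would still leave ANCOVA ahead by 16, 15, 11, 8 and 4 points at r = 0, 0.1, 0.3, 0.5 and 0.7, and would not settle whether the arms are compared at all.

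**Conclusion.** The SAP has an underspecified model; an error in the analysis has not been demonstrated. What can be concluded unconditionally is that it names no within-child term and no baseline covariate for data that are paired by child. The faults in standard errors and type I error are conditional on ordinary between-subject error being used, and their size on r.

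The case for changing the method does not depend on which reading is right. In the scenario examined, ANCOVA had more power than either version of the arm-by-time test at every correlation tried. Its lead over a correct repeated-measures test narrows as r rises. The absolute power figures rest on the assumed 1 SD advantage, normality and equal SDs. Even with ANCOVA, power is below 50% for that effect at r of 0.5 or less, so the change makes better use of a small sample but does not make the sample adequate.

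**What to change.** Replace the ANOVA sentence with one model per outcome, fitted across all three arms: month-3 score on arm, with the child's own baseline score on that measure as covariate. Report TF-CBT vs TAU, CCT vs TAU and CCT vs TF-CBT, each with a 95% CI. State that any within-arm pre-post comparison will be a paired test or a model with time as a within-child factor. If a 3 x 2 layout is kept as a supplement, name its error terms and do not interpret the arm main effect averaged over baseline and month 3 as a treatment effect.

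The cost is SAP wording and one degree of freedom per model. Baseline scores are already scheduled by the protocol, so no new data are needed. The change does not address selection from analysing completers only, which is a separate matter.

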1. PURPOSE OF THE STUDY

a. Brief Summary

This study is designed to examine three treatment conditions for traumatized youth: Cue-Centered Treatment (CCT), Trauma-Focused Cognitive-Behavioral Therapy (TF-CBT), and Treatment as Usual (TAU) to determine which treatment works most effectively for which youth. We would like to determine feasibility of training on the treatment interventions. In addition, this study aims to inform development of systems of care for chronically traumatized youth.

Objectives

We hope to determine whether 1) TF-CBT and CCT will have better outcomes than TAU, 2) Child characteristics predict better outcome in either TF-CBT or CCT and to identify which phases of treatment are most effective, and 3) Imaging findings will be predictors of improved outcome. This research is important because while there are many existing trauma interventions for youth, little is known about what is most essential in those interventions. This study will shed light on what components of treatment are most effective. Furthermore, there are minimal guidelines on how to select the most appropriate intervention for a particular child. This study will contribute to that knowledge by informing which interventions are suited best for which youth.

b. Rationale for Research in Humans

This project will allow the investigation of three existing treatment interventions for children with post-traumatic stress disorder. The purpose is to inform treatment selection based on most effective treatment components and child characteristics.

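### The SAP specifies no between-arm test, although the first objective is that TF-CBT and CCT do better than TAU

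*SAP*

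**What the plan says.** Protocol section 1a sets a comparative first objective: "We hope to determine whether 1) TF-CBT and CCT will have better outcomes than TAU". Section 2a gives the design that could answer it: "Participants will be randomly assigned to one of three treatment conditions: TF-CBT, CCT, or TAU". Section 5m adds a general intention, "Analysis will be within and between groups", but gives no model, outcome or contrast.

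The SAP's Planned Analyses consist of a single sentence. It opens "Factorial ANOVAs comparing baseline to month 3 (end of treatment) total scores on all outcome measures", lists the instruments, and closes "Behavior Rating Inventory of Executive Function) will be conducted for each treatment arm". The only comparison it names is baseline against month 3. Under Planned Sample Size the analysis set is limited to children who completed treatment: "The sample size is 8 participants for the CCT group, 8 for TF-CBT, and 6 for TAU".

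**The concern.** Objective 1 is a claim about differences between randomised arms, and the SAP describes no test of such a difference. Change within an arm mixes any treatment effect with natural recovery, regression to the mean and retest effects. The TAU arm is there to separate these, and it can do so only if the arms are compared directly.

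Two problems follow.

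- **Literal reading.** The analysis yields three sets of pre-post tests. The natural misuse is to read significance in CCT and non-significance in TAU as evidence that CCT is better. It is not, and with arms this small and unequal the pattern arises often when the treatments do not differ.
- **Generous reading.** If an arm-by-time model was intended, the reader still cannot tell which test or contrast decides objective 1, so it could be chosen after the results are known.

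**Working it through.** **Inputs from the documents.** The analysis set is 8 (CCT) + 8 (TF-CBT) + 6 (TAU) = 22 completers, against 135 planned in Protocol section 5a (22/135 = 16%). The documents give no expected change, SD, pre-post correlation, alpha or power, so there is no stated figure to reproduce. Everything below assumes two-sided tests at 0.05 and one outcome, over ranges of the missing quantities.

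**Step 1: literal per-arm reading.** Suppose all arms have the same true change, so there is no treatment difference. Let d be the mean change divided by the SD of change. The power of a paired t-test with n children is P(|T| > t(0.975, n−1)), where T is noncentral t with n−1 df and noncentrality d√n. Write p8 and p6 for n = 8 and n = 6. With independent arms, the chance that at least one active arm is significant while TAU is not is

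P = [1 − (1 − p8)²] × (1 − p6).

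| d | p8 | p6 | P |
|---|---|---|---|
| 0 | 0.050 | 0.050 | 0.093 |
| 0.3 | 0.114 | 0.093 | 0.196 |
| 0.5 | 0.232 | 0.171 | 0.340 |
| 0.8 | 0.496 | 0.356 | 0.481 |
| 1.0 | 0.681 | 0.507 | 0.443 |
| 1.2 | 0.828 | 0.655 | 0.335 |
| 1.5 | 0.951 | 0.833 | 0.167 |
| 2.0 | 0.998 | 0.971 | 0.029 |

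For example, at d = 0.5: [1 − 0.768²] × 0.829 = 0.410 × 0.829 = 0.340.

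**Step 2: what a between-arm test would do.** Simulation with 40,000 runs per setting: bivariate normal scores, SD 1 at both times, n = 8/8/6, both active arms shifted equally, pre-post correlation r. Effects and half-widths are in SDs of the score.

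| Quantity | r = 0.3 | r = 0.5 | r = 0.7 |
|---|---|---|---|
| Arm-by-time F (2, 19 df), size | 0.049 | 0.048 | 0.047 |
| Arm-by-time F, power at 1.0 SD | 0.292 | 0.396 | 0.596 |
| ANCOVA arm F (2, 18 df), size | 0.051 | 0.048 | 0.049 |
| ANCOVA arm F, power at 1.0 SD | 0.407 | 0.481 | 0.645 |
| ANCOVA CCT − TAU, power at 1.0 SD | 0.437 | 0.509 | 0.663 |
| ANCOVA CCT − TAU, power at 0.5 SD | 0.149 | 0.167 | 0.222 |
| Mean 95% CI half-width, CCT − TAU | 1.10 | 1.00 | 0.82 |

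**Step 3: hand check of the half-width.** Ignoring chance baseline imbalance, it is about t(0.975, 18) × √(1 − r²) × √(1/8 + 1/6) = 2.101 × √(1 − r²) × 0.540. This gives 1.08, 0.98 and 0.81 SD at r = 0.3, 0.5 and 0.7. The simulated values are slightly larger because they include the imbalance.

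**Step 4: simple cross-check.** A two-sample t-test of change scores, 8 against 6, has exact power of 14%, 28% and 40% at differences of 0.5, 0.8 and 1.0 SD of change. It needs about 1.65 SD for 80% power.

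**The case against.** **The word factorial implies arm-by-time.** A factorial ANOVA needs at least two factors, and baseline against month 3 inside one arm has only one. Read with Protocol section 5m and objective 1, an arm-by-time model is plausible. This stands as a possible explanation of the wording, but it does not fill the gap. The closing per-arm clause points the other way, no arm factor is named, and even a stated 2-df interaction would not say which arm differs from TAU.

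**The feared inference is not in the SAP.** True: the SAP has no decision rule, so Step 1 measures a misuse that the text permits but does not prescribe.

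**Step 1 uses the event with the larger probability.** Objective 1 names both active treatments. If both must be significant and TAU not, the chance is p8² × (1 − p6) = 4%, 16%, 23%, 24% and 15% at d = 0.5, 0.8, 1.0, 1.2 and 1.5. The 9% at no change also counts significant worsening; counting only improvement in the active arms gives 4.7%. Nor is unequal arm size the whole cause: with 8 children in every arm the figures would be 32%, 38% and 29% at d = 0.5, 0.8 and 1.0, so low power and two chances against one carry much of it. These points affect the size of the illustration, not the conclusion.

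**ANCOVA is partly a preference.** Both between-arm tests hold size near 5%, so ANCOVA's advantage is efficiency. Naming the interaction and its TAU contrasts would also cure the gap.

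**No model will settle objective 1 with 22 completers.** Often true, but low power does not justify leaving the test undefined. A wide interval on the right contrast shows the uncertainty, whereas a within-arm p-value can hide it.

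**Conclusion.** The concern holds, and the SAP must be corrected on this point. As written, it defines no test of the trial's first objective, and the protocol's general statement of intent does not supply one. Followed literally, the analysis could show an apparent advantage over TAU in at least one active arm, with no true difference, in 34% to 48% of trials at standardised changes of 0.5 to 1.0. Outside that range the chance is lower: 9% at no change and 3% at 2.0.

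These figures rest on assumed changes, normal data, independent arms, one outcome and two-sided 0.05 tests. The textual finding rests on none of them. A properly specified between-arm analysis would have about 15% to 22% power for CCT minus TAU at 0.5 SD and 44% to 66% at 1.0 SD, over r from 0.3 to 0.7.

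**What to change.** For each outcome, specify one ANCOVA of the month-3 score on treatment arm and baseline score. Report CCT minus TAU, TF-CBT minus TAU and CCT minus TF-CBT with 95% CIs. Label within-arm changes as descriptive and state that no efficacy claim rests on them. State that the analysis set is treatment completers only, so the contrasts are not fully protected by randomisation.

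Three additions would help:

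- **Primary outcome and deciding contrasts.** Three contrasts on the five scores listed in the SAP make 3 × 5 = 15 comparisons.
- **A multiplicity rule** for those comparisons.
- **A statement of timing.** The SAP is dated 9/18/20, after the July 2020 end scheduled in the protocol, and already gives completer counts by arm. That does not show that outcomes had been seen, but contrasts added now should be labelled post hoc if they had been.

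The cost is SAP wording and a few lines of code, with no new data. The downside is wide intervals, about ±0.8 to 1.1 SD for CCT minus TAU, so objective 1 will often remain unsettled. The change does not cure the completers-only restriction.
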